7.6 Acquisition of study products

FP Conjugate Vaccine, Trimer 4571, Trimer 6931, PBS diluent and Adjuplex adjuvant are provided by the VRC, NIAID, DAIDS. Once a CRS is protocol registered, the pharmacist can obtain study products from the NIAID Clinical Research Products Management Center (CRPMC) by following the ordering procedures outlined in Pharmacy Guidelines and Instructions for DAIDS Clinical Trials Networks.

7.7 Study Product Accountability

The CRS pharmacist is required to maintain complete records of all study products. The pharmacist of record is responsible for maintaining randomization codes and randomization confirmation notices for each participant in a secure manner.

7.8 Final Disposition of study product

For US clinical research sites, all unused study products must be returned to the clinical research products management center (CRPMC) after the study is completed or terminated unless otherwise instructed by the study sponsor. For non-US clinical research sites, all unused study products must be destroyed after the study is completed or terminated unless otherwise instructed by the study sponsor. The procedures are included in the Pharmacy Guidelines and Instructions for DAIDS Clinical Trials Networks.

8 Clinical procedures

8.1 Screening

Screening for eligibility will be performed after informed consent has been obtained and properly documented before enrollment. Screening evaluations and sample collection include medical history review, physical exam, and any clinical laboratory tests as detailed in the Schedule of procedures ([Appendix A](#), [Appendix B](#), [Appendix C](#) and [Appendix D](#)) needed to confirm eligibility. Persons assigned female sex at birth who are of reproductive potential will be given a pregnancy test. Additional assessments of health may be conducted at screening based on clinical judgment.

If screening evaluations suggest a current concerning health condition or infection, then appropriate laboratory tests may be conducted to evaluate these conditions. Additional assessments of health may be conducted at screening based on clinical judgment. Screening evaluations for specific eligibility criteria ([Section 5](#)) must be completed within the time interval specified prior to enrollment for the given parameter and may be repeated, as needed, to confirm eligibility.

An Assessment of Understanding (AoU) will be completed prior to enrollment. Records will be kept documenting the reasons that screened participants did not enroll or were ineligible.

8.2 Definition of Study Day and Study Visit

Study Day 0 is defined as the day of the first vaccination. A study visit may be conducted remotely, such as via phone, text message, email, or other electronic means, in lieu of, or in combination with, in-person visits. As long as they are completed within the visit window (see [Appendix E](#) and [Appendix F](#)), procedures for a study visit can be completed over multiple days. The procedures for documenting remote visits and out of window visits are described in the HVTN 303 SSP.

8.3 Reactogenicity Assessments

Pre-Vaccine Administration: Medical history and evaluations including vital signs and planned injection site evaluation are performed prior to each vaccine administration.

Post-Vaccine Administration Follow-Up in Clinic: Following each vaccine administration, participants will be observed for a minimum of 30 minutes post injection, vital signs will be recorded, the injection site will be inspected for

evidence of local reaction, and any evidence of systemic symptoms will be assessed. Participants will be contacted on the day after each study injection as indicated on the Schedule of Procedures ([Appendix A](#), [Appendix B](#), [Appendix C](#) and [Appendix D](#)).

Post-Clinic Follow-Up: Participants are asked to record symptoms on a daily basis using an electronic participant diary. Signs and symptoms considered to represent reactogenicity from the vaccine include systemic events of increased body temperature, fatigue, generalized myalgia, generalized arthralgia, headache, chills, nausea, and local events at the injection site, including pain/tenderness, induration, erythema, and bruising. Participant diaries will be reviewed by a clinician and reconciled for accuracy and completeness.

Participants will be given a thermometer for oral temperature measurement, a ruler, and provided access to the electronic diary. Participants will be encouraged to use the preferred electronic diary but will have the option to use a paper diary. The paper diary, if used, will be transcribed into the study database and stored in the participant file for monitoring purposes. The participant will use the diary to record daily their highest temperature as well as local and systemic signs and symptoms for 10 full days following each study vaccination. Participants will be provided training on diary completion, proper thermometer usage, and the use of the measuring device to measure any injection site induration and/or erythema.

In LOA #3 for protocol version 1.0 (distributed to the sites on Dec 14, 2022) the reactogenicity assessment period was increased from 7 days to 10 days. However, as vaccinations were permanently discontinued on January 13, 2023, the change in post-vaccine reactogenicity assessment period was no longer applicable and was not implemented. The reactogenicity assessment period of the previously vaccinated participants remained 7 days following vaccine administration.

Remote or in-person contact between the participant and the site staff should take place on the day after each study injection. The reactogenicity assessment period is 10 days following vaccine administration. Clinicians will follow and collect resolution information for any reactogenicity signs and symptoms that have not resolved within 10 days.

Any post vaccination reaction grade 2 or higher will be assessed by a clinician within 48 hours after onset, unless the reaction is improving and/or has completely resolved. Additionally, other clinical concerns may prompt a study visit based on the judgment of a study clinician.

Given the first-in-human use of the various adjuvanted study products alone or in prime-boost regimens, the HVTN 303 PSRT may recommend that skin biopsies be obtained if unusual skin reactions following vaccinations are reported. Sites are

encouraged to have a process in place for this optional study procedure. Refer to the HVTN 303 SSP for further details.

Clinicians or site staff may photograph the skin reactions to document unusual skin findings.

8.4 Leukapheresis for Part B participants

Only participants who received two vaccinations in Part B (Groups 7-8) and who consent to leukapheresis will undergo leukapheresis at 10 months +/- 2 months post–last vaccination in order to collect blood cells for research.

~~Part B (groups 6-8) participants who consented to leukapheresis (see Sections 2.7 and 5.1.3) will undergo leukapheresis at 2 weeks post last vaccination in order to collect blood cells of special interest for research.~~ This procedure requires participants meeting additional eligibility criteria (see Section 5.1.3). Collection of PBMC via leukapheresis will be performed in accordance with the standard practices of the participating apheresis center. Ideally, in this procedure, approximately 1 to 4 liters of blood will be processed over 1 to 2 hours using peripheral veins for venous access. The blood will be anti-coagulated in accordance with standard practice of the apheresis center.

Post procedural safety assessments will be performed in accordance with the standard practices of the participating apheresis center. Additionally, the participant will be advised to contact the study site if they experience any AEs following the procedure.

8.5 Visit windows and missed visits

The schedule of visits and evaluations performed at each visit are shown in [Appendix A](#), [Appendix B](#), [Appendix C](#) and [Appendix D](#). Visit windows are shown in [Appendix E](#) and [Appendix F](#). The procedures for documenting missed visits and out of window visits are described in the HVTN 303 SSP. If the missed visit is one that required safety assessments or local safety labs, HVTN CRS staff should attempt to bring the participant in for an interim visit as soon as possible.

8.6 Monitoring for COVID-19 symptoms

Participants will be monitored for symptoms of COVID-19 at each study visit (see [Appendix A](#), [Appendix B](#), [Appendix C](#) and [Appendix D](#)).

8.7 Monitoring for HIV infection

Study participants will be tested for HIV infection periodically throughout the study, as indicated in the schedules included in [Appendix A](#), [Appendix B](#), [Appendix C](#) and [Appendix D](#). The Laboratory Program (or approved diagnostic laboratory) will follow the HVTN HIV testing algorithm (see HVTN Laboratory Center MOP), which is able to distinguish vaccine-induced antibody responses from actual HIV infections. Participants will be promptly informed and counseled if they become HIV-infected during the study and will be referred for treatment (see Section [5.2.2](#)).

Study participants will receive regularly scheduled counseling regarding avoidance of HIV infection in accordance with the most recent Centers for Disease Control and Prevention HIV counseling guidelines.

Although the study vaccine will not cause HIV infection, it may induce antibodies detectable by standard HIV infection screening techniques. This is referred to as VISp. The following steps will be taken to protect participants from adverse consequences associated with VISp:

- Participants will be counseled to avoid HIV antibody testing outside of the HVTN CRS during study participation.
- Participants can receive HIV diagnostic testing from the CRS following their last scheduled visit until they are told they do not have VISp.
- Participants with VISp will be periodically offered free-of-charge poststudy HIV diagnostic testing (per the HVTN poststudy HIV testing algorithm) as medically/socially indicated (approximately every 6 months) unless or until HIV antibody testing is no longer standard in clinical settings.
- Unless participants request that their names be removed, the names of all participants in HVTN studies are entered into a secure VISp registry in order to verify that an individual received an HIV vaccine (and therefore has the potential for VISp) and to qualify former participants for post study HIV testing to distinguish between VISp and HIV infection. Information in the VISp registry is not used for research.

8.8 Early termination visit

If a participant terminates participation in the study early for any reason, the site PI should consider if the following assessments are appropriate: end-of-study HIV test, CBC with differential, serum chemistry, physical examination, social impact assessment and, if indicated, a pregnancy test (see [Appendix A](#), [Appendix B](#), [Appendix C](#) and [Appendix D](#)). For participants with HIV infection, please see

Section [5.2.2](#). If the site PI has questions regarding a termination visit, they should consult with the PSRT.

9 Safety and adverse events

9.1 Adverse events

Unsolicited AEs will be collected over a period of 28 days after each vaccination. All collected AEs are captured in the clinical database on the appropriate case report form (CRF). Clinic staff should evaluate every AE to determine if (1) the AE meets the requirements for expedited reporting (see Section 9.2.1), (2) if the AE meets the criteria for a safety pause/prompt AE review (see Section 9.5), (3) if the AE meets the criteria for an MAAE, and (4) if the AE is a potential immune-mediated medical condition (PIMMC) or an AESI. A sample list of AESIs and PIMMCs is provided in [Appendix M](#).

In addition, a limited set of AEs will be collected and reported for 12 months following any vaccine administration.

- SAEs/EAEs,
- AESIs,
- MAAEs (defined as any AEs leading to an unscheduled visit to a healthcare professional),
- Safety lab-related AEs,
- AEs leading to early participant withdrawal or early discontinuation of study vaccine(s) administration.

AEs will be graded according to the Division of AIDS (DAIDS) Table for Grading the Severity of Adult and Pediatric Adverse Events, Corrected Version 2.1 (<https://rsc.niaid.nih.gov/clinical-research-sites/daids-adverse-event-grading-tables>), with the following exceptions:

- Unintentional Weight Loss is required to be reported as an AE only if it is considered to be potentially deleterious to the participant's health (see HVTN 303 SSP).
- Creatinine is required to be reported as an AE only if it is gradable per the increase from local lab ULN parameter. Do not grade elevated creatinine based on the change from the baseline parameter.
- Do not grade creatinine clearance or estimated glomerular filtration rate (eGFR) based on the change from the baseline parameter. Do not grade on the basis of eGFR if there is clinical concern for kidney injury.

- Injection Site Erythema or Redness and Injection Site Induration or Swelling will not consider surface area and interference with usual social and functional activities, such that:
 - Grade 1 is: 2.5 to < 5 cm in diameter;
 - Grade 2 is: ≥ 5 to < 10 cm in diameter;
 - Grade 3 is: ≥ 10 cm in diameter OR Ulceration OR Secondary infection OR Phlebitis OR Sterile abscess OR Drainage;
 - Grade 4 is: Potentially life-threatening consequences (eg, abscess, exfoliative dermatitis, necrosis involving dermis or deeper tissue)
- For severity grading of the solicited bruising parameter at the product administration site, the definitions based on size of the largest diameter and listed for the “Injection Site Erythema or Redness” will be used. The severity grade definition for “Bruising” provided under the Dermatologic Clinical Conditions will be used only for unsolicited AEs involving bruising at other body locations.

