1.6 Duration per participant

For participants in Part A (Groups 1-5): 52 weeks of scheduled clinic visits.

~~For participants in Part B (Groups 6 and 7): 100 weeks of scheduled clinic visits.~~

~~For participants in Part B (Group 8): 96 weeks of scheduled clinic visits.~~

On January 13, 2023, a protocol memo was distributed informing the clinical research sites that all vaccinations in HVTN 303 were permanently discontinued. Procedures specified for remaining follow-up visits have been revised. Duration for Part A participants remained unchanged. Duration for Part B participants (for Groups 6 -8) is 56 weeks.

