3.1 Primary objectives and endpoints

Primary objective 1:

To evaluate the safety and tolerability of the following regimens in healthy adults:

- Adjuvanted FP conjugate vaccine administered IM at a dose of 25 or 200 mcg,
- Adjuvanted Trimer 6931, administered IM at a dose of 100 or 200 mcg,
- Adjuvanted Trimer 4571 administered IM at 200 mcg, or
- Prime-boost vaccination regimen of FP conjugate and Trimer 4571.

Primary endpoint 1:

Local and systemic reactogenicity signs and symptoms, laboratory measures of safety, and adverse and serious adverse events.

SAEs, medically attended adverse events (MAAEs), adverse events of special interest (AESIs) and AEs leading to early participant withdrawal or permanent discontinuation which will be collected throughout the study and for 12 months following any receipt of study product. Additionally, all adverse events will be collected for 28 days after any receipt of study vaccination. All safety lab related adverse events will be collected throughout duration of study.

Primary objective 2:

To evaluate the ability of FP-conjugate and Trimer 4571 vaccines to elicit FP-specific binding antibodies in Part B participants.

Primary endpoint 2:

Magnitude and response rate of serum antibody binding of FP and envelope trimer antigens as measured by the MSD assay 2 weeks after the last vaccination.

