¹²Research Samples: Blood draw volumes for each tube type shown.

¹³PBMC for assays & storage: To be collected only from participants who will not undergo leukapheresis.

¹⁴Leukapheresis: Will only be collected from participants who agreed to provide this sample type and who have met leukapheresis eligibility criteria (see Section 8.4). A pregnancy test must be performed and confirmed negative within 72 hours prior to leukapheresis (see also: footnote 8). For participants who decide not to provide leukapheresis samples, 119 mL of ACD blood will be collected instead of leukapheresis.

¹⁵Skin biopsies will be obtained if unusual skin reactions following vaccinations are reported (see Section 8.3)

¹⁶Collection of research samples has been discontinued since March 13, 2023

¹⁷Vaccinations have been permanently discontinued since January 13, 2023

Appendix D Follow-up schedule of procedures for Part B (Tables for Group 6, Group 7, and Group 8) post termination of vaccinations

Part B, Group 6

Schedule of Procedures Part B: Group 6 ^a																	
Visit Number	100	101	102	103	110	111	112	116	117	118	122	123	124	129	130	131	132
Study Week	0	1	2	12	13	14	24	25	26	36	37	38	48	49	50	56	
Study Day	-56 to 0	0	7	14	84	91	98	168	175	182	252	259	266	336	343	350	392
Procedure	Vac 1																
Study Procedures	Tube	Screen ¹															
Assessment of Understanding		✓															
Informed Consent		✓															
Physical Exam ²		✓	✓	✓	✓	✓	✓	✓	✓	✓	✓	✓	✓	✓	✓	✓	
Medical History ³		✓	✓	✓	✓	✓	✓	✓	✓	✓	✓	✓	✓	✓	✓	✓	
Concomitant Medications ⁴		✓	✓	✓	✓	✓	✓	✓	✓	✓	✓	✓	✓	✓	✓	✓	
Vaccination ^{5,17}		✓															
Reactogenicity Diary ⁶		✓															
Follow-Up Contact ⁷		✓															
Adverse Events (AEs)		✓	✓	✓	✓	✓	✓	✓	✓	✓	✓	✓	✓	✓	✓	✓	
AESIs/MAAEs/SAEs		✓	✓	✓	✓	✓	✓	✓	✓	✓	✓	✓	✓	✓	✓	✓	
COVID-19 symptom check		✓	✓	✓	✓	✓	✓	✓	✓	✓	✓	✓	✓	✓	✓	✓	
Contraception status assessment ⁸		✓	✓														
Social impact assessment		✓	✓	✓	✓	✓	✓	✓	✓	✓	✓	✓	✓	✓	✓	✓	
Social impact questionnaire						✓											
HIV Risk Reduction Counseling ⁹		✓				✓				✓		✓			✓	✓	
Clinical Labs																	
Pregnancy Test (urine or serum) ^{9,10}		✓	✓														
CBC/Differential ¹⁰	EDTA	3	3	3	3	3	3	3	3	3	3	3	0	0	0	0	
ALT/Creatinine ¹⁰	SST	4	4	4	4	4	4	4	4	4	4	4	0	0	0	0	
HIV screening test ^{10,11}	SST	5	0	0	0	0	0	0	0	0	0	0	0	0	0	0	
HBsAg/anti-HCV ¹⁰	SST	5	0	0	0	0	0	0	0	0	0	0	0	0	0	0	
HIV diagnostic test	EDTA	0	0	0	0	0	10	0	0	10	0	0	10	0	0	10	20
Research Samples ^{12,15,16}																	

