Yellow shaded columns represent visits without any sample collection. If these visits have already happened, please collect data in the CRFs. Otherwise, please skip these visits.

1 Screening evaluations at Visit 100 are performed no more than 56 days before Day 0.

2 A complete physical exam is performed at screening and last clinic visit, to include height, weight, vital signs, and clinical assessments of head, ears, eyes, nose, and throat; neck, lymph nodes; heart; chest; abdomen; extremities; neurological function; and skin. At other visits, a targeted physical exam will be performed as needed, based on participant report or indications of illness.

3 Medical history: A complete history is performed during screening. At enrollment and subsequently, an interim medical history may be performed.

4 Concomitant medications, including prescription and non-prescription drugs, vitamins, topical products, alternative/complementary medicines, recreational drugs, vaccinations, and allergy shots are recorded during screening, at enrolment, and at each subsequent clinic visit.

5 Vaccination (in clinic assessments): At least 30 minutes after each study injection and prior to clinic discharge, participants will have vital signs taken and the injection site will be assessed, and systemic symptoms will be assessed.

6 Reactogenicity diary: Participants will complete a 7-day diary as noted in Section 8.3. If any solicited reactogenicity is unresolved by Day 10, it will continue to be reviewed with the participant at each visit until resolved.

7 Follow-Up Contact: Participants will be contacted by telephone the day after each vaccination which might not necessarily be within the visit window for vaccination.

8 Contraception status assessment and pregnancy test are required only for participants who were assigned female sex at birth and are capable of becoming pregnant. Pregnancy test may be performed on urine or blood specimens. Persons who are NOT capable of becoming pregnant due to total hysterectomy or bilateral oophorectomy (verified by medical records), or menopause (no menses for \geq 1 year) are not required to undergo pregnancy testing. For persons who are confirmed pregnant, pregnancy testing is not required, unless clinically indicated.

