#### **10.4.2 AEs and SAEs**

AEs will be summarized using Medical Dictionary for Regulatory Activities (MedDRA) System Organ Class and preferred terms. Tables will show by treatment arm (in Part A and Part B) the number and percentage of participants experiencing an AE within a System Organ Class or within preferred term category by severity or by relationship to study product. For the calculations in these tables, a participant with multiple AEs within a category will be counted once under the maximum severity or the strongest recorded causal relationship to study product. Formal statistical testing comparing arms is not planned since interpretation of differences must rely heavily upon clinical judgment.

A listing of SAEs reported to the Division of AIDS (DAIDS) Regulatory Support Center (RSC) Safety Office will provide details of the events including severity, relationship to study product, time between onset and last vaccination, and number of vaccinations received.

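### For unsolicited AEs outside the long-term set, Part A and Part B percentages may rest on different observation times, because the Appendix D AE row runs past the 28-day limit and the SAP tables set no onset window

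*Protocol*

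**What the plan says.** Protocol 9.1: "Unsolicited AEs will be collected over a period of 28 days after each vaccination". Primary endpoint 1 (protocol 3.1, repeated in SAP section 4) has the same limit: "Additionally, all adverse events will be collected for 28 days after any receipt of study vaccination". Beyond that, 9.1 provides that "a limited set of AEs will be collected and reported for 12 months following any vaccine administration". That set is SAEs/EAEs, AESIs, MAAEs, safety-lab AEs, and AEs leading to withdrawal or discontinuation.

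The schedules carry two rows, one for AEs in general and one for AESIs, MAAEs and SAEs. In Appendix B (Part A) the general row stops at Day 28 and the other runs to Day 364. In Appendix D (Part B after vaccination stopped) the general row is as long as the other in all three groups, and no footnote limits it. A footnote to Appendix D says of visits without sample collection: "If these visits have already happened, please collect data in the CRFs. Otherwise, please skip these visits".

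On duration, protocol 1.6 says "For participants in Part A (Groups 1-5): 52 weeks of scheduled clinic visits" and "Duration for Part B participants (for Groups 6 -8) is 56 weeks".

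SAP 10.4.2 tabulates the number and percentage of participants with an AE by arm in both parts, where "a participant with multiple AEs within a category will be counted once under the maximum severity". Neither 10.4.2 nor the table list in 11.2 restricts AEs by onset date. SAP 10.4.2 also says that no formal test between arms is planned.

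**The concern.** A Part B site working from its schedule could go on recording every kind of AE well after the 28-day period has closed. A Part A site working from its own schedule stops at Day 28. Two Part B sites could also differ within one arm if one follows 9.1 and the other follows Appendix D.

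The SAP then tabulates the percentages by arm for both parts. Groups 5 and 6 received the same single dose (200 mcg Trimer 4571), and Groups 2 and 7 the same first dose (200 mcg FP conjugate), so a reader will want to compare them. Part of any difference could be observation time and not product, in a trial whose stated primary goal is to identify safety concerns.

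**Working it through.** **Durations.** The last Appendix D visit is Day 392, and 392 / 7 = 56 weeks, which reproduces the stated Part B duration. For Part A, 364 / 7 = 52 weeks, also as stated.

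**The 28-day limit in Part B.** One dose at Day 0 closes the period at Day 28. A second dose at target Day 28 closes it at Day 56. Two doses were given to 5 of 10 participants in Group 7 and 6 of 9 in Group 8, so 11 in all. Scheduled post-screening visits after Day 56 number 13 of 16 (Group 6), 15 of 22 (Group 7) and 14 of 21 (Group 8).

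**Length of the rows (ticks legible in the text).**

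| Schedule | Post-screening visits | General AE row | AESI/MAAE/SAE row |
|---|---|---|---|
| Part A, Appendix B | 11 | 4 | 11 |
| Group 6, Appendix D | 16 | 15 | 15 |
| Group 7, Appendix D | 22 | 22 | 22 |
| Group 8, Appendix D | 21 | 20 | 20 |

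**Can safety labs explain the later ticks?** Safety-lab AEs must be collected long term and have no row of their own. By the daily blood volumes, CBC and ALT/creatinine draws (3 + 4 = 7 mL) run to Week 37 in Groups 6 and 7 and Week 36 in Group 8. Post-screening visits with such draws number 11, 17 and 16. Granting a tick to every one of them leaves 15 - 11 = 4, 22 - 17 = 5 and 20 - 16 = 4 ticks at visits without safety labs. Some of those have no sample at all and are skipped if not already done: by zero volume, two in Group 6, one in Group 7 and three in Group 8. That still leaves at least 4 - 2 = 2, 5 - 1 = 4 and 4 - 3 = 1.

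**Size at the extreme.** 392 / 28 = 14. Let r be the rate per person-year of unsolicited AEs outside the long-term set. The documents give no such rate, so r = 1 with range 0.5 to 2 is an assumption. With a constant hazard, P(at least one) = 1 - exp(-r × days / 365.25).

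| r | 28 days | 392 days |
|---|---|---|
| 0.5 | 3.8% | 41.5% |
| 1 | 7.4% | 65.8% |
| 2 | 14.2% | 88.3% |

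At r = 1, the expected number with at least one such AE is 3 × 0.074 = 0.2 of 3 in Group 5 and 10 × 0.658 = 6.6 of 10 in Group 6, with no product effect.

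**Effect on tables that mix all AEs.** Part A still collects SAEs, AESIs and MAAEs to Day 364. If a share s of AEs falls in those categories (also an assumption), Part A observes the equivalent of 28 + 336s days. At a total rate of 1 per year:

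- s = 0.25: 112 days, 26.4%, against 65.8% in Part B
- s = 0.5: 196 days, 41.5%, against 65.8%

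**With a 28-day onset filter.** Observation is 28 days for one dose in every arm, a ratio of 1:1 with Part A, and about 56 days for two doses, a ratio of 2:1. The remaining 2:1 comes from the number of doses.

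**The case against.** The other side has several good points.

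- Lab AEs and AEs leading to withdrawal need a row, and the general AE row is the natural place. In Part A the row stops exactly where safety labs stop. This explains many later Part B ticks, and leukapheresis or the large blood draw may explain some late ones in Groups 7 and 8. It does not explain the late Group 6 visits without labs, and no footnote says that the row narrows.
- The tick columns are imperfect in the extracted text. The Group 6 physical exam row should span 17 columns and shows 15. Individual cells need checking in the PDF. Lost ticks would make the AE row look shorter, however, so they do not weaken the finding that it runs late.
- SAP section 4 restates the 28-day limit, and 11.3 lists SAEs/EAEs, AESIs and MAAEs separately. But section 4 is a collection rule and 11.3 gives listings for the SMB reports. Neither filters the by-arm tables.
- Part A arms have 3 participants, so only 0, 33, 67 or 100% can occur, and 11.2 includes a related-events table. Both reduce the scope for misreading without removing it.

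A reader might infer that Part B sites recorded all AEs at every visit for 56 weeks. The documents do not support that. Sample-free visits not yet done are skipped. Version 2.0 is dated September 21, 2023, when Part B participants (enrolled November 3 to December 20, 2022) were at Days 275 to 322, so Appendix D could govern only the last visits. Earlier visits ran under Appendix C, whose AE row also goes well past Week 4 but was written for doses planned to Week 44 or 48. That the row was simply left uncut is a plausible guess and no more. Continued AE checks after a safety stop could have been intended.

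**Conclusion.** The inconsistency is real and limited in scope. Section 9.1, endpoint 1 and the Part A schedule agree on 28 days. The Appendix D general AE row does not, and the SAP tables contain nothing that would absorb the difference.

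The consequence is conditional. It concerns unsolicited AEs outside the long-term set, in descriptive percentages that set Part A arms beside Part B arms, and only to the extent that sites followed the Part B schedule rather than 9.1. The tempting summary that the by-arm AE tables compare 4 weeks with 56 is too strong. The three Part B arms share one follow-up length, the serious and medically attended categories are followed long term in both parts, and no formal AE comparison is planned.

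The 14-fold ratio and the 7% against 66% are therefore an upper illustration. They rest on an assumed rate, a constant hazard and full adherence to the schedule. The point merits correction because the remedy is cheap and the affected contrasts (Group 5 v 6, Group 2 v 7) are the natural ones by product.

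**What to change.** 1. **Protocol, Appendix D.** Reconcile the general AE row with 9.1 and endpoint 1, for example by a footnote that after 28 days from the last dose the row captures only the long-term categories. Deleting the later ticks outright is not advisable, since lab AEs and AEs leading to withdrawal would then have no row.
2. **SAP 10.4.2 and 11.2.** Restrict the by-arm all-AE tables to onset within 28 days of a dose. Tabulate the long-term set separately, noting that safety-lab follow-up is longer in Part B. List other later AEs without comparing arms.
3. **Table notes.** State the number of doses received, because two-dose participants in Groups 7 and 8 still contribute about 56 days.

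The cost is one footnote, one onset-date filter and one added table. No new data are needed, and the SAP change works even if all visits are complete. The downside is that some later non-serious, non-attended Part B AEs move from the tables to a listing.
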